7.2.1.8.2 Infections

If a patient develops fever (\geq 38.5°C) or any sign of infection during the study, deferiprone must be interrupted immediately, and neutrophil count should be obtained and monitored more frequently; every 2 days if ANC <1.5 x 10^9 /L (ANC < 1.0 x 10^9 /L for a black patient). Therapy with deferiprone can be re-initiated once all symptoms have been resolved and it is deemed safe by the investigator.

7.2.1.8.3 Decreased Serum Ferritin

As deferiprone is an iron chelator, treatment might decrease the levels of serum ferritin to a level that could fall below normal limits. The levels of serum ferritin will therefore be monitored during this study. A patient who is found to have low serum ferritin may be prescribed iron supplements, based on investigator judgment.

7.2.2 Laboratory Measurements

Analyses will be performed at a central laboratory, with the exception of the weekly hematology assessments which may be performed at a local laboratory or, with sponsor approval, at the patient's home by a visiting study nurse. Investigators must interpret each report promptly (preferably within 24 hours) and must document their review by signing or initialing and dating it. Any laboratory values that fall outside a clinically accepted range, or that differ significantly from previous values, must be assessed for clinical significance, and

must be marked by the investigator as either "CS" (clinically significant) or "NCS" (not clinically significant). Any clinically significant abnormalities or changes that are not part of a larger medical condition that is already recorded must be further explained on the laboratory report and documented as an adverse event in the eCRF.

The following laboratory tests will be performed:

Hematology: hemoglobin, total WBC count, ANC, MCV, and platelet count	Screening and weekly after start of dosing until Month 9
Blood chemistry: Total protein, GGT, lactate dehydrogenase (LDH), sodium, potassium, chloride, fasting glucose, bilirubin (total, direct, and indirect), AST, ALT, albumin, blood urea nitrogen, calcium, creatinine, uric acid, alkaline phosphatase, amylase, serum ferritin, blood iron, zinc, and copper	Screening and each visit after start of dosing until Month 9
Urinalysis: pH, specific gravity, glucose, protein, ketones, blood, and (if indicated by the dipstick results), sediment microscopy. If there is blood in the urine or three or more "plus signs" for protein, samples must be sent for microscopy.	Screening and Months 3, 6, and 9
Pregnancy testing (women of childbearing potential only): Both urine and serum tests at baseline; only serum test at each other time point	Each visit

7.2.3 Other Safety Measurements

7.2.3.1 Physical Examination

Physical examination will consist of an examination of head, ears, eyes, nose, throat and neck, respiratory system, cardiovascular system, gastrointestinal system, musculoskeletal system, neurological systems (central and peripheral), and skin, nails, hair, and scalp. Examinations will be performed at screening, baseline, and Months 2, 4, 6, and 9. Any clinically significant abnormalities noted prior to the screening visit will be recorded as medical history, any noted between screening and the first dose of study medication will be recorded as medical events, and any that are noted post–Dose 1 will be recorded as AEs.

Body weight (without shoes) will be measured at screening and Month 9. Height will be measured at screening only.

7.2.3.2 Vital Signs

Supine and standing heart rate, supine and then standing blood pressure, and body temperature will be taken. Blood pressure should always be measured after a minimum 3-minute resting period, and using the same arm each time if possible. Systolic and diastolic blood pressures are to be recorded from one measurement. At the Day 0 visit (baseline), 3 sets of orthostatic vital signs (pulse and blood pressure), first in the supine and then in the standing position, are to be conducted prior to start of treatment, with 10- to 30-minute intervals between measurements. A single set of measurements is to be performed at all other time points.

Vital signs will be measured at each site visit. Clinically significant out-of-range values for vital signs will be reported as AEs (see Section 7.2.1.1).

7.2.3.3 Electrocardiogram

A standard 12-lead ECG will be performed at screening and Month 9. At a minimum, the following parameters will be assessed: HR, PR, QRS, QT, QTcF, and QTcB. The results will be interpreted by the investigator, and the overall interpretation will be documented.

7.2.3.4 Columbia Suicide Severity Rating Scale

Current guidelines for clinical trials of investigational neurological drugs call for the prospective assessment of suicidal ideation and behavior, whereby the physician actively queries the patient rather than relying on the patient to report any occurrences spontaneously. The Columbia Suicide Severity Rating Scale (C-SSRS) is designed to track suicidal adverse events across a treatment trial. The scale assesses a range of ideation and behavior, as well as intensity of ideation. The Baseline/Screening version of the scale will be used at baseline, and the Since Last Visit version will be used at post-baseline visits.

The C-SSRS will be completed at each visit from baseline to Month 9 by the qualified investigator or delegate.

7.2.3.5 Concomitant Medications

The following information about prior and concomitant medications is to be recorded:

- All medications used within the 3 months prior to screening
- Any medications that the patient continues to take during the study
- Any medications that the patient starts to take during the study

The name, dose, route, frequency, indication, and stop and start dates of all medications used during the study must be noted in the source documents and eCRFs, as well as whether or not the medication was used to treat an AE.

Information on concurrent medications will be obtained at every site visit and at the followup telephone call.

7.2.4 Procedures in Case of Pregnancy

If a patient becomes pregnant during the course of the study, she will be immediately withdrawn. The pregnancy is to be immediately reported to the sponsor, and information about the pregnancy is to be recorded on the appropriate form and in the patient's eCRF. The patient will be followed to determine the outcome, and any premature termination of the pregnancy will be reported. Upon delivery, the child will be examined for any adverse symptoms or congenital anomalies. Follow-up information on the status of the mother and child will be forwarded to the sponsor no later than 8 weeks following the delivery.

If the partner of a male patient becomes pregnant during the course of the study, or if the fetus may have been exposed to the patient's study products either through maternal exposure or through transmission via semen following paternal exposure, the pregnancy must be reported to the sponsor, and information about the pregnancy must be recorded on the appropriate form and in the patient's eCRF. If the partner provides consent for follow-up of the pregnancy, she will be followed until the delivery of the child, and information on the delivery status of the mother and child will be forwarded to the sponsor no later than 8 weeks following the delivery date.

Any SAE occurring as a result of a post-study pregnancy that the investigator believes may have been caused by the study product or by a protocol procedure will be reported to the sponsor as described in Section 7.2.1.6.

7.3 Pharmacokinetics Measurements

7.3.1 Collection of Samples

Blood (5 mL at each time point) and cerebrospinal fluid (0.5–1.0 mL) for analyses of deferiprone and deferiprone 3-O-glucuronide will be collected. Details on sample collection will be provided in a separate laboratory manual.

All patients: At baseline and Month 3, a total of 3 blood samples will be collected: pre-dose, at 2 hours post-dose (\pm 45 minutes), and at 4 hours post-dose (\pm 45 minutes), with a minimum of 1 hour between samples.

Note: For the subset of 18 patients who have agreed to undergo CSF sampling, the post-dose blood samples at Month 3 will be taken at 2 hours (\pm 15 minutes) and 4 hours (\pm 15 minutes) post-dose, to be aligned with the timing of the CSF samples.

Subset of 16 patients: At Month 1, a total of 18 blood samples per patient will be collected: pre-dose and at 0.25, 0.5, 0.75, 1.0, 1.33, 1.66, 2.0, 2.33, 2.66, 3.0, 3.5, 4.0, 5.0, 6.0, 8.0, 10.0, and 12.0 hours post-dose.

Subset of 18 patients: At Month 3, patients who agree to undergo a spinal tap will contribute one sample of CSF. Six of the 18 patients will provide this sample pre-dose, 6 will provide it at 2 hours post-dose (\pm 15 minutes), and 6 will provide it at 4 hours post-dose (\pm 15 minutes). The time of sample collection will be assigned prior to the Month 3 visit.

7.3.2 Processing of Samples

Details on the processing of blood and CSF samples will be provided in the laboratory manual.

8 STUDY COMMITTEES

An independent Data Safety Monitoring Board (DSMB) will be established to monitor the safety of patients during the course of the study. Members of the DSMB will be responsible for overseeing the conduct of the trial, and will be empowered to recommend stopping the trial if, in their judgment, continuation is not ethically acceptable on the grounds of safety.

Death or a life-threatening event in any study patient which is deemed by either the investigator or the sponsor to be at least possibly related to the study medication will trigger an evaluation by the DSMB for recommending stopping the study. Details will be provided in the DSMB charter. No study-stopping decision will be made without prior consultation with the sponsor.

The operating model and the frequency of the interim safety review meetings will be laid out in the DSMB charter. The DSMB will be constituted prior to the enrolment of any patients into the study, and its members will be notified of any changes to the protocol or the study conduct. The DSMB will be informed of any substantive changes to the protocol that could affect patient safety prior to their implementation.

9 STATISTICAL ANALYSIS

9.1 Endpoints

9.1.1 Primary Endpoint

The primary endpoint is the change from baseline to Month 9 in the motor examination subscale (Part III) of the Movement Disorder Society-Unified Parkinson's Disease Rating Scale (MDS-UPDRS).

9.1.2 Secondary Endpoints

- Change from baseline to Month 9 in the following measures:
 - Total score on the MDS-UPDRS
 - Scores on the individual subscales Part I (non-motor experiences of daily living),
 Part II (motor experiences of daily living), and Part IV (motor complications) of the MDS-UPDRS
 - o Combined scores from Parts II and III of the MDS-UPDRS
 - Overall cognitive function, as assessed by the Montreal Cognitive Assessment (MoCA) test
 - Pharmacodynamics measures of the following oxidative stress biomarkers: total antioxidant status, lipid peroxidation (malondialdehyde), protein carbonyls, 8-OHdG, glutathione, superoxide dismutase
 - Pharmacodynamics measures of the following inflammatory factor biomarkers: TNF alpha and IL-6
- Time elapsed until the need for rescue medication

9.1.3 Exploratory Endpoints

The following Mechanism of Action (MOA) biomarkers will be examined to evaluate whether specific genotypes of enzymes that play a role in Parkinson's disease affect the potential disease-modifying action of deferiprone:

- D544E polymorphisms of the glycoprotein ceruloplasmin
- V158M polymorphisms of the enzyme catechol O-methyltransferase
- Ceruloplasmin levels (to be analyzed depending on the outcomes of the primary and/or secondary efficacy endpoints)
- Ceruloplasmin ferroxidase activity (to be analyzed depending on the outcomes of the primary and/or secondary efficacy endpoints)

9.1.4 Safety Endpoints

- Adverse events (AEs): Frequency, intensity, time to onset, duration, and relatedness to study drug
- Serious adverse events (SAEs): Frequency, intensity, time to onset, duration, and relatedness to study drug
- Number of discontinuations due to AEs
- Laboratory measures (hematology, blood chemistry, and urinalysis)

- ECG
- Change from baseline in vital signs (the average of the three sets of vital signs collected at the baseline visit will be considered the baseline value)
- Physical examination
- Assessment of suicidality (as per the Columbia Suicide Severity Rating Scale)

9.1.5 Pharmacokinetics Endpoints

The following PK parameters will be determined for deferiprone and its 3-O-glucuronide metabolite in the subset of patients who undergo extensive PK sampling:

- C_{max}
- T_{max}
- AUC_{0-t}
- AUC_{0- ∞}
- λ_Z
- T_{1/2}

The parameters of λ_Z , $T_{1/2}$, and $AUC_{0-\infty}$ will be determined only in patients in whom the log-linear terminal phase can clearly be defined. In addition, Cl_{tot}/F and VD/F will also be determined for deferiprone.

9.2 Determination of Sample Size and Study Power

There is no formal sample size and power calculation. Based on preliminary data from other investigators, it is estimated that 28 subjects per dosage will be sufficient to provide meaningful assessment of each dosage for the study objectives.

9.3 Study Populations

Four study populations for analysis will be defined: Intent-to-Treat (ITT), Per-Protocol (PP), Safety, and Pharmacokinetics. All efficacy endpoints will be analyzed for the ITT population, which represents the primary analysis population. The primary efficacy endpoint will also be analyzed for the PP population, which represents the secondary analysis population.

9.3.1 Intent-to-Treat Population

The ITT population is defined as all randomized patients who received at least one dose of study drug and have a baseline and at least one post-baseline efficacy assessment. All efficacy endpoints will be analyzed for the ITT population.

9.3.2 Per Protocol Population

The PP population is defined as all randomized patients who complete the study, have no major protocol violations, and have an efficacy assessment at the end of the study. Prior to database lock, protocol violations will be reviewed for their seriousness, and patients with major violations will be excluded from the PP population. Only the primary efficacy endpoint will be analyzed for the PP population.

9.3.3 Safety Population

The Safety population will include all randomized patients who received at least one dose of study drug.

9.3.4 Pharmacokinetics Population

The Pharmacokinetics population will include all patients who have sufficient PK data to derive at least one PK parameter.

9.4 Data Analysis Plan

Separate statistical analysis plans (SAPs) will be prepared, one for the efficacy and safety analyses, and either one or two others for the pharmacokinetics and the pharmacokinetics/ pharmacodynamics analyses. The SAPs will detail the specifications given below, and will be approved prior to database lock. Any changes in the planned statistical methods will be documented in the final study report.

9.4.1 Planned Analyses

Data from all patients who were randomized to receive placebo will be combined into one group for the statistical analyses. Thus, there will be 5 treatment groups in the efficacy and safety analyses: placebo and 300 mg, 600 mg, 900 mg, and 1200 mg deferiprone.

9.4.1.1 Patient Disposition and Drug Exposure

Patient disposition, based on the ITT population, will be summarized descriptively. Data will include the number and percentages of patients who were screened, enrolled, completed the study, and withdrawn (including reasons for withdrawals).

For each patient, the number of doses taken will be computed from the study drug dispensing and accountability eCRFs obtained at each visit. The extent of exposure to the study medication as well as compliance during the study will be summarized with descriptive statistics.

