3 STUDY DESIGN

3.1 Description of Study Design

This is a multi-center, randomized, double-blind, placebo-controlled, dose-ranging study in 140 patients who have been diagnosed with typical Parkinson's disease within the last 3 years and are currently taking antiparkinsonian medication. Screening will be conducted within 30 days prior to the start of dosing. At baseline, eligible participants will be randomized to one of four dosage cohorts, and within each cohort will be further randomized in a 4:1 ratio to receive either active product or placebo. The assigned study product will be taken twice-daily (b.i.d.), at least 8 hours apart, for 9 months. Dosages are as follows:

- Cohort 1: 300 mg deferiprone delayed release tablets (n=28) or placebo (n=7)
- Cohort 2: 600 mg deferiprone delayed release tablets (n=28) or placebo (n=7)
- Cohort 3: 900 mg deferiprone delayed release tablets (n=28) or placebo (n=7)
- Cohort 4: 1200 mg deferiprone delayed release tablets (n=28) or placebo (n=7)

Patients will return to the site at Months 1, 2, 3, 4, 5, 6, and 9, and will receive a follow-up telephone call at Month 10. Safety will be assessed at each site visit and at the follow-up call; efficacy measures will be assessed at baseline and Months 3, 6, and 9; and sparse pharmacokinetics (PK) sampling will be done on all patients at baseline and Month 3. In addition, an optional subset of 16 patients will undergo extensive blood sampling for PK analysis at Month 1, and an optional subset of 18 patients will each provide one sample of cerebrospinal fluid (CSF) for drug level analysis at Month 3. (No selection will be done to enroll these subsets: all patients will be asked if they are willing to provide either or both of these types of samples, and they will be enrolled as they come until the total number of subjects is reached for each subset.) For safety reasons, all patients will have their absolute neutrophil count monitored weekly after the start of dosing. This procedure may be done either at either the study site or a local laboratory, or, with sponsor approval, at the patient's home by a visiting study nurse.

Any patient who withdraws before completing treatment will be requested to return within one month for an Early Termination visit, at which time the procedures normally scheduled for the Month 9 visit will be conducted.

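### Patient disposition is based on the ITT set, which cannot supply the screened and enrolled counts and omits withdrawals with no post-baseline efficacy assessment

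*Protocol*

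**What the plan says.** Protocol Section 9.4.1.1 sets the base for the disposition table: "Patient disposition, based on the ITT population, will be summarized descriptively". The next sentence lists the contents, namely the "number and percentages of patients who were screened, enrolled, completed the study, and withdrawn", with reasons for withdrawal.

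Section 9.3.1 defines the base in two parts: "The ITT population is defined as all randomized patients who received at least one dose of study drug", who must also "have a baseline and at least one post-baseline efficacy assessment".

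On timing, Section 3.1 states that "efficacy measures will be assessed at baseline and Months 3, 6, and 9". It also provides for those who stop early: "Any patient who withdraws before completing treatment will be requested to return within one month for an Early Termination visit". That visit carries the Month 9 procedures.

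A wider set exists but is not used for disposition. Section 9.3.3 states: "The Safety population will include all randomized patients who received at least one dose of study drug".

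**The concern.** A disposition table accounts for everyone who entered the study and shows where each person left it. A base set that requires follow-up data removes some of the people the table is meant to report. Anyone with no efficacy assessment after baseline drops out of the withdrawal count and the denominator together, so withdrawal looks lower and completion higher than among the patients randomised.

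The trial seeks the dose with the best balance of benefit and risk (Section 3.3), and safety and tolerability is a secondary objective (Section 2.2). Each of the five analysis groups has 28 patients, and withdrawn patients are not replaced (Section 4.5.2). A few missing withdrawals can therefore move a group's percentage noticeably.

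**Working it through.** **1. Planned numbers.** Section 5.2 gives four cohorts of 28 active and 7 placebo patients: 4 × (28 + 7) = 140, of whom 4 × 28 = 112 are on deferiprone and 4 × 7 = 28 on pooled placebo. This reproduces the protocol's total. The protocol states no dropout rate.

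**2. Who is in the ITT set.** Setting Section 9.4.1.1 beside Section 9.3.1:

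| Patient | In ITT? | Needed for disposition? |
|---|---|---|
| Screened, not randomised | No | Yes (screened) |
| Randomised, not dosed | No | Yes (enrolled, withdrawn) |
| Dosed, left, never rated after baseline | No | Yes (enrolled, withdrawn) |
| Dosed, left early, rated at Early Termination | Yes | Yes |
| Dosed, left after a Month 3 or Month 6 rating | Yes | Yes |

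Section 7.1 counts the MDS-UPDRS, the MoCA and the biomarkers as efficacy measurements, and all post-baseline measurements fall at Months 3, 6 and 9 or at Early Termination. The Month 1 and Month 2 visits include none, so they cannot bring a patient into the ITT set.

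**3. Effect on the withdrawal percentage.** Let N be the number randomised, W all withdrawals, and u the withdrawals with no efficacy assessment after baseline. The rate over all randomised patients is W/N. The ITT-based rate is (W − u)/(N − u). The difference is

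W/N − (W − u)/(N − u) = u(N − W) / [N(N − u)].

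This is zero when u = 0 and positive otherwise, provided at least one patient completes.

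**4. Illustrative range.** Assumptions: N = 140; all are dosed; 5%, 10% or 15% leave before Month 3; a further 10% (14 patients) leave later, after a rating; and none, half or all of the early leavers have no Early Termination rating. Half-patients come from the percentages.

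| Early leaving | All randomised | ITT, none unrated | ITT, half unrated | ITT, all unrated |
|---|---|---|---|---|
| 5% | 21/140 = 15.0% | 15.0% | 17.5/136.5 = 12.8% | 14/133 = 10.5% |
| 10% | 28/140 = 20.0% | 20.0% | 21/133 = 15.8% | 14/126 = 11.1% |
| 15% | 35/140 = 25.0% | 25.0% | 24.5/129.5 = 18.9% | 14/119 = 11.8% |

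The understatement runs from 0 to 25.0 − 11.8 = 13.2 percentage points, with 0 to 21 withdrawals lost. The formula agrees for the last cell: 21 × 105 / (140 × 119) = 0.132. In that cell, completion would read 105/119 = 88.2% instead of 105/140 = 75.0%.

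**5. One group of 28.** With assumed counts of 8 withdrawals, 4 of them never rated again, 8/28 = 28.6% becomes 4/24 = 16.7%. If all 8 are rated at Early Termination, nothing changes.

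**The case against.** The strongest reply has four parts.

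- **Early Termination visit.** A reader might infer that the ITT set drops early leavers as such. It does not. Someone who stops in week 2, returns and is rated stays in the set. This stands: only leavers who also have no Early Termination rating are lost, and the loss may be zero. However, patients are asked to return (Section 3.1) and should do so (Section 4.5), so attendance is not assured.
- **Adverse event summaries.** A reader might also infer that adverse event withdrawals vanish from the tolerability results, most of all at poorly tolerated doses. The protocol does not support that. Section 9.4.1.4 presents, by treatment group, patients exposed, patients withdrawn and withdrawals due to adverse events, gives reasons for withdrawal, and adds a listing of adverse event withdrawals. No efficacy condition is attached, and Section 9.1.4 makes such discontinuations a safety endpoint. A concentration of losses in particular doses would be an assumption. This largely stands. But Section 9.4.1.4 names no analysis set for these summaries, so their withdrawal count could differ from that in the disposition table without explanation.
- **Few undosed patients.** Randomisation and the first dose take place at the same baseline visit (Section 5.1). This stands, and that group should be small.
- **Loose wording.** Asking for screened numbers suggests that a wider base was intended, and a gap between enrolled and completed plus withdrawn would be visible. This is plausible, but the sentence names the ITT set. Section 9.4 says the analysis plans will elaborate the protocol's specifications, so the wrong base could carry through.

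**Conclusion.** Wrong as written. The two sentences of Section 9.4.1.1 cannot both be carried out: the named set contains no screen failures and not necessarily everyone enrolled. Followed literally, it understates withdrawal and overstates completion whenever a patient leaves with no efficacy assessment after baseline. Under the assumed dropout rates above, the understatement is between 0 and about 13 percentage points. Its actual size turns on Early Termination attendance, which the protocol cannot tell us.

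The fault is one of reporting, mainly in a single descriptive table. It does not affect the primary efficacy test, and tolerability by dose does not rest on this table alone.

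**What to change.** Replace the base in Section 9.4.1.1. Report screening on all screened patients. Report enrolled, completed and withdrawn, with reasons, over all randomised patients by treatment group. Show the number excluded from each analysis set and why. Naming the analysis set for the withdrawal counts in Section 9.4.1.4 would let the two presentations be reconciled.

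The cost is one sentence in the protocol, carried into the analysis plan. No new data or procedures are needed. The reported withdrawal rate may look less favourable.
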